9.3.5 Clinical Laboratory Assessments

Blood samples for serum chemistry and hematology will be obtained after an 8-hour fast, except for the Week 2 and Week 5 liver function tests. The study investigator should monitor subjects during the study for signs of hepatic abnormality potentially meeting the stopping criteria (Section 11).

The investigator will review clinical laboratory test results as they become available, for determination and documentation of clinical significance (if there are out of range values). The investigative site will contact the medical monitor for any liver function test results that potentially meet the stopping criteria. Possibly drug related or clinically relevant abnormal values of uncertain causality must be repeated. Persistently abnormal laboratory values should be followed at the investigator's discretion. Clinical labs may be repeated for eligibility assessments. Abnormal liver function tests (specified in section 11) must be repeated within 48-72 hours.

Hematology assessments will include total white blood cell count, differential (neutrophils, lymphocytes, monocytes, eosinophils, and basophils), hemoglobin, hematocrit, red blood cell count, platelet count and HbA1c (at Visit 1).

Serum chemistry assessments will include electrolytes (bicarbonate, calcium, chloride, phosphorous, potassium, sodium, and magnesium), enzymes (alkaline phosphatase, aspartate aminotransferase, alanine aminotransferase, lactate dehydrogenase, and gamma-glutamyl transferase), and other (albumin, total bilirubin, direct bilirubin, indirect bilirubin, creatinine, glucose, triglycerides (at screening), total protein, blood urea nitrogen, and uric acid).

Qualitative urinalysis will include pH, specific gravity, glucose, ketones, protein, blood, leukocyte esterase, urobilinogen, nitrites, and reflex microscopy.

All women of childbearing potential will receive urine pregnancy tests (\(\beta\)-human chorionic gonadotropin).

The urine drug panel will include cannabinoids, opioids, and benzodiazepines; an alcohol screen will also be performed with a breathalyzer.

Hepatitis and HIV screen includes: Hepatitis B surface antigen, hepatitis C antibody, and HIV. If the screening hepatitis C antibody test result is reactive, a nucleic acid test for HCV RNA should be performed for confirmation of chronic infection. If the screening HIV test is positive, a confirmatory Western Blot test should be performed to confirm HIV status.

9.3.6 Sheehan Suicidality Tracking Scale (S-STS)

The standard version of the S-STS (Sheehan 2014[2]) is a 16-item scale that assesses the seriousness of suicidality phenomena on a Likert-type scale (0 to 4) ranging from 0 = "not at all" (0) to 4 = "extremely". It also assesses the frequency of key phenomena and the overall time spent in suicidality. The standard version is available in identical clinician- and subject-rated formats. The S-STS accommodates a wide range of time frames. In clinical trials, the frequently used variants are "in the past week", "in the past month", "since the last visit", "lifetime look back", and "in the past day".

The S-STS maps to both the C-CASA, and to all of the categories in the FDA Draft Guidance documents of both 2010 and 2012, and in addition provides coverage for all suicidal phenomena presented in the draft FDA guidance. The S-STS has been studied and validated against other instruments used for the assessment of suicidality in a study, and been shown provide at least equal sensitivity to detecting suicidal ideation and behavior (Sheehan 2014 [1]).

Suicidality identified after baseline will be recorded as an adverse event.

9.4 Safety and Pharmacovigilance

9.4.1 Adverse Events – Relationship to Investigational Product

An adverse event is any untoward, undesired, unplanned clinical event in the form of signs, symptoms, disease, or laboratory or physiological observations occurring in a human being participating in a clinical study with an Aptinyx investigational product, regardless of causal relationship. A pre-existing condition is one that is present before investigational product dosing and is reported as part of the subject's medical history. Pre-existing conditions should be reported as an adverse event only if the frequency, intensity, or character of the pre-existing condition worsens during the course of the study.

Laboratory abnormalities are not considered adverse events unless they are associated with clinical signs or symptoms, or require medical intervention. However, a laboratory abnormality (e.g., a clinically significant change detected on clinical chemistry, coagulation, hematology, urinalysis) that is independent from the underlying medical condition and that requires medical or surgical intervention, or leads to investigational product interruption or discontinuation, must be considered an adverse event.

For each reported adverse event, an investigator must assess the relationship to investigational product using the following scale:

Unrelated

- Does not follow a known response pattern to the suspect investigational product (if response pattern is previously known).
- Can clearly be explained by the known characteristics of the subject's clinical state or other modes of therapy administered to the subject.

Unlikely Related

- The temporal sequence from dosing of the investigational product suggests that a relationship is unlikely.
- Follows a response pattern that is unlike that of the suspect investigational product (if response pattern is previously known).
- Could be reasonably explained by the subject's clinical state or other modes of therapy administered to the subject.

Possibly Related

- Follows a reasonable temporal sequence from dosing of the investigational product.
- May follow a known response pattern to the suspect investigational product (if response pattern is previously known).
- Could also be reasonably explained by the subject's clinical state or other modes of therapy administered to the subject.

Probably Related

- Follows a reasonable temporal sequence from dosing of the investigational product.
- Could not be reasonably explained by the known characteristics of the subject's clinical state or any other modes of therapy administered to the subject.
- Is confirmed by improvement on stopping or slowing dosing of the investigational product, if applicable.

When an assessment is not provided, the event will be treated as possibly related for purposes of regulatory reporting.

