9.3.4 Electrocardiogram

Electrocardiograms (5-minute duration) will be collected after 5 minutes of supine rest and prior to blood sample collection, if possible. The device will be a Spaulding electrocardiogram device that acquires a 12-lead electrocardiogram continuously at each time point for up to 5 minutes. The 5 minutes of electrocardiogram data will be converted into a summary electrocardiogram (simulated 10-second electrocardiogram) for each electrocardiogram time point and submitted to the designated electrocardiogram laboratory cardiologists for measurements and diagnoses as though it were a standard 10-second electrocardiogram. Electrocardiograms may be repeated for eligibility assessments.

The investigator or qualified sub-investigator will review all electrocardiogram interpretations and interval duration measurements for clinical significance. Standard electrocardiogram parameters will be measured. Clinically significant, abnormal 12-lead electrocardiograms should be repeated. Clinically significant electrocardiogram changes should be recorded as an adverse event.

The Spaulding electrocardiogram device should be used for all assessments during the study unless it is non-operational, in which case another electrocardiogram may be performed locally and transmitted to Spaulding for central reading via printout.

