11 STOPPING CRITERIA

Subjects will be withdrawn from the treatment period of the study if any of the following criteria are met. Repeat testing must be completed within 48-72 hours:

Repeated results (i.e. values confirmed by repeat testing):

- Serum total bilirubin $\geq 2.5 \text{ mg/dL}$, or
- Subject meets one of the following criteria
 - ALT or AST >3 x ULN, or
 - ALT or AST \geq 3 x ULN, and total bilirubin \geq 2 x ULN, or
 - ALT or AST \geq 3 x ULN, with the appearance of fatigue, nausea, vomiting, right upper quadrant pain, or tenderness, fever, rash, or eosinophilia (>5%), or
 - Alkaline phosphatase $\geq 2x$ ULN.

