10.1 Adverse Events

Treatment-emergent adverse events (TEAEs) will be those occurring during or after administration of the first dose of study drug until 30 days after the final dose of study drug. Due to the nature of this study, the date and time of first dose of study drug was not collected on the CRF. Therefore, the following algorithm will be used to determine if the adverse events are treatment-emergent:

- Earliest Possible AE Start Date ≥ Baseline Visit and Study Drug Dispensation and
- Latest Possible AE Start Date ≤ 30 Days After the Final Dose of Study Drug

Adverse events that started on the Baseline Visit (Study Day 1) that are the result of abnormal clinically significant electrocardiograms (ECGs) or clinical laboratory tests collected prior to study drug dispensation will not be considered TEAEs.

The following System Organ Class (SOC) AEs for abnormal clinically significant clinical laboratory tests will be reviewed to determine if the AE is not treatment-emergent:

- Investigations
- Infections and infestations (with the Preferred Term = "Urinary tract infection")

AEs that started prior to first dosing of study drug, but become worse in severity after receiving study drug will be considered treatment-emergent. The determination of whether or not an adverse event is classified as "treatment emergent" (i.e. TEAE) is not dictated by the classification of "relationship to study drug" collected on the CRF, but rather by the temporal relationship of the adverse event to the administration of study drug.

A related study drug TEAE is defined as any TEAE with at least a possible relationship to the study drug as assessed by the investigator or that is missing the assessment of causal relationship whose relationship to the study drug could not be ruled out. Relationships of "possibly related", "probably related", or missing are collected on the CRF, then those adverse events will be considered related study drug TEAEs. If the "unrelated" or "unlikely related" are collected on the CRF, then those adverse events will be considered not related study drug TEAEs.

Severity is assigned to each adverse event collected on the CRF. Maximum severity has the following order: "life threatening", "severe", "moderate", and "mild" as possible collection options on the CRF. A missing severity will be treated as "unknown" for analysis purposes.

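### Section 9.4.1 makes a confirmed, symptom-free Section 11 liver result an adverse event at Week 2 but not at Week 4 or Week 5

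*Protocol*

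**What the plan says.** **When a laboratory result is an AE.** Protocol Section 9.4.1 sets a default: "Laboratory abnormalities are not considered adverse events unless they are associated with clinical signs or symptoms, or require medical intervention". The next sentence gives a mandatory rule for an abnormality "that is independent from the underlying medical condition": one that requires medical or surgical intervention, "or leads to investigational product interruption or discontinuation, must be considered an adverse event".

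**What a liver result does to treatment.** Section 11 provides that "Subjects will be withdrawn from the treatment period of the study if any of the following criteria are met". The listed values must be confirmed by repeat testing within 48-72 hours. Several criteria need no symptoms: ALT or AST >3 x ULN, total bilirubin ≥2.5 mg/dL, and alkaline phosphatase ≥2 x ULN.

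**When liver tests are drawn.** After baseline they are scheduled at Week 2 (Section 10.3.1), Week 4 or early termination (Section 10.3.2) and Week 5 (Section 10.4). The second 2-week drug supply is dispensed at Week 2. Unused drug is handed back at Week 4 (Section 6.1). Week 5 is 7 days later.

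**What else happens to an abnormal result.** Section 9.3.5 has the site contact the medical monitor about any liver result that may meet the stopping criteria. It also says "Persistently abnormal laboratory values should be followed at the" investigator's discretion. Under Section 12.6.2, laboratory results that the investigator considers clinically important are identified, but not as AEs.

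**How the SAP counts.** SAP Section 10.1 counts TEAEs up to 30 days after the final dose. SAP Section 10.2 tabulates laboratory values by visit, counts potentially clinically significant (PCS) values, and plots peak liver values in eDISH figures, all without reference to AE status.

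**The concern.** For a liver result with no symptoms and no intervention, the only remaining route to AE status in Section 9.4.1 is an effect on study drug. That route depends on where the subject is in the visit schedule, not on the finding. Two subjects with the same confirmed ALT can be classified differently only because one sample was drawn while capsules remained to be taken.

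The panels affected are the ones at the end of exposure. For a completer, Week 4 and Week 5 are the only scheduled liver panels after the full 4 weeks of dosing, and safety and tolerability of multiple dose levels is a stated objective. A result that is not an AE receives no relatedness, severity or outcome assessment, so it cannot enter the TEAE or related-TEAE tables. Someone comparing those tables with the PCS counts could not tell whether the investigator saw no event or the recording rule excluded one.

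**Working it through.** The plan gives no figure to reproduce. The check applies Section 9.4.1 to one test case at each scheduled post-baseline liver panel.

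**Test case.** ALT or AST >3 x ULN, confirmed on repeat, no symptoms, no intervention required, independent of the underlying condition. This meets a Section 11 threshold.

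**Inputs.** Visit windows come from Protocol Table 3: Day 14 ± 2, Day 28 ± 2, Day 35 ± 2. The repeat test follows 48-72 hours later, that is 2 to 3 days (Sections 9.3.5 and 11). Planned dosing ends at Day 28.

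**Formulas.** Earliest repeat = earliest draw + 2. Latest repeat = latest draw + 3. Planned dosing days left = 28 − repeat day.

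| Panel | Draw (Day) | Repeat (Day) | Drug status at repeat | Route met in 9.4.1 | AE? |
|---|---|---|---|---|---|
| Week 2 | 14 − 2 = 12 to 14 + 2 = 16 | 12 + 2 = 14 to 16 + 3 = 19 | 28 − 19 = 9 to 28 − 14 = 14 planned dosing days left | Section 11 withdrawal leads to discontinuation | Must be |
| Week 4 | 28 − 2 = 26 to 28 + 2 = 30 | 26 + 2 = 28 to 30 + 3 = 33 | Drug returned at the visit | None | Default: no |
| Week 5 | 35 − 2 = 33 to 35 + 2 = 37 | 33 + 2 = 35 to 37 + 3 = 40 | Off drug | None | Default: no |

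The drug-action route can operate at 1 of 3 panels. It cannot operate at 3 − 1 = 2 of 3.

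**Is the late result outside the analysis window?** No. With a last dose on Day 28, the SAP's TEAE window runs to Day 28 + 30 = 58. The latest Week 5 draw (Day 37) and its repeat (Day 40) both fall inside it. The recording rule, not the analysis window, leaves the result out.

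**Does another passage close the gap?** The opening definition in Section 9.4.1 includes laboratory observations among possible AEs, but the following paragraph narrows it expressly for laboratory abnormalities. Section 9.3.5 requires repeat testing and contact with the medical monitor, not AE recording. Section 12.6.2 asks only that important results be identified. None of these makes the Week 4 or Week 5 test case an AE.

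**The case against.** The strongest reply is that little is lost. The Section 11 repeat and the contact with the medical monitor do not depend on AE status. SAP Section 10.2 reports Week 4 and Follow-up values by treatment group, shifts to the highest post-baseline result, PCS counts by visit and overall (with the same >3 x ULN cut-off for ALT and AST), and eDISH plots. AE tables and laboratory tables count different things. The rule is identical in all arms, and phase 1 reported no laboratory TEAEs, though in small groups of healthy volunteers. All of this stands. It limits the harm but does not make the classification consistent.

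A reader might infer more than the documents support:

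- **That laboratory AEs depend wholly on stopping drug.** They do not. Symptoms make a result an AE at every visit, and so does a need for intervention. Only the remaining case is affected.
- **That SAP Section 10.1 conflicts with the protocol.** It says "The following System Organ Class (SOC) AEs for abnormal clinically significant clinical laboratory tests will be reviewed", but the sentence goes on to say that the purpose is to decide whether an AE is not treatment-emergent. The context is Day 1 tests taken before drug was dispensed. It sorts recorded AEs by timing and sets no recording rule.
- **That the ECG rule contradicts Section 9.4.1.** Section 9.3.4 says "Clinically significant electrocardiogram changes should be recorded as an adverse event". That is a different rule for a different assessment: a contrast, not a conflict.
- **That late liver findings go unfollowed.** Follow-up of persistent abnormalities is discretionary, but AE follow-up under Section 9.4.3 is also to a resolution satisfactory in the investigator's opinion. SAP Section 5.4.1 provides for repeat follow-up visits.

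**Conclusion.** The point holds in a narrow form. A confirmed liver result that meets a Section 11 threshold, has no symptoms, needs no intervention and is independent of the underlying condition must be an AE at Week 2. At Week 4 or Week 5 it meets no trigger. The gap covers 2 of the 3 scheduled post-baseline panels, both inside the TEAE window.

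The consequence is under-counting and inconsistent classification of late liver findings in the TEAE and related-TEAE tables, with no relatedness or outcome assessment. The laboratory values are not lost. A reader might also infer a bias between doses, but a rule that is the same in every arm gives no evident reason for one.

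The conclusion assumes that sites read Section 9.4.1 literally and that dosing has ended by the Week 4 visit. If some sites record such results anyway, the inconsistency moves from between visits to between sites. The documents give no event rate, so the number of affected subjects cannot be stated and may be small or zero.

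**What to change.** Amend the default sentence in Section 9.4.1 so that it excepts any post-dose laboratory result that meets a Section 11 threshold and is confirmed on repeat. State that such a result is recorded as an AE through follow-up, whether or not study drug is stopped. Editing the default sentence itself matters, because adding a new sentence beside it would leave the section contradicting itself. The wording should also cover the repeat of a Week 5 sample, which falls 2 to 3 days after the last scheduled visit.

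Leave the Section 11 thresholds, the stopping rule and the handling of all other laboratory results unchanged. A wider rule that made every clinically significant laboratory result an AE is not justified here. In a Type 2 diabetes population with HbA1c allowed up to 11%, it could bring in glucose and urine findings that reflect the underlying disease.

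The cost is one amended protocol sentence, a note to sites, and a few more AE records under Investigations. Each record would then carry relatedness, severity and outcome, and the same confirmed liver finding would be classified the same way at every post-dose visit.

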9.4.2 Recording Adverse Events

A "pre-existing" condition is one that is present before investigational product dosing and is reported as part of the subject's medical history. Pre-existing conditions should be reported as an adverse event only if the frequency, intensity, or character of the pre-existing condition worsens during the course of the study. Adverse events will be collected from the time the informed consent is signed to the end of the subject's participation in the study.

Subjects should be instructed to report all potential adverse events to the investigator, and, queried in a non-leading manner, without specific prompting (e.g., "How are you feeling?"). The site study staff should assess emerging symptoms of dissociative reaction similar to those caused

by NMDA antagonists including memory impairment, disturbance in time, body or environmental perception, stilted speech, emotional withdrawal, impaired coordination, motor retardation, bizarre reasoning or illusory experiences in any sensory perception, or confused state; such symptoms may be captured as adverse events.

To avoid vague, ambiguous, or colloquial expressions, all adverse events should be recorded in standard medical terminology rather than in the subject's own words. Each adverse event will also be described in terms of duration (start and stop date), severity, relationship to investigational product, action(s) taken, and outcome. Diagnoses (rather than symptoms) should be recorded wherever possible.

9.4.3 Reporting Adverse Events

All adverse events must be documented, evaluated, and reported in the source documents and eCRF. Adverse event collection begins after the subject has completed the informed consent and continues until the subject's participation in the study ends. Ongoing adverse events should be followed to a satisfactory resolution in the investigator's opinion. Subjects should be instructed to report all adverse events to the investigator. In addition, the investigator should seek to elicit any clinical or objective reactions by specific questioning (e.g., "How have you been feeling?") and as appropriate by examination. Information on all adverse events should be recorded on the eCRF. All clearly related signs, symptoms, and results of diagnostic procedures performed in relation to an adverse event should be grouped together and recorded as a single diagnosis.

9.4.3.1 Severity of Adverse Events

All adverse events will be assessed for severity, using the following general grading scale:

Mild: Transient or mild discomfort (<48 hours); no medical intervention/therapy required.

Moderate: Mild to moderate limitation in activity – some assistance may be needed; no or minimal medical intervention/therapy required.

Severe: Marked limitation in activity, some assistance usually required; medical intervention/therapy, required hospitalization possible.

Life threatening: Extreme limitation in activity, significant assistance required; significant medical intervention/therapy required, hospitalization, or hospice care probable.

When changes in the severity of an adverse event occur more frequently than once a day, the maximum severity for the experience that day should be noted. If the severity category changes over a number of days, then those changes should be recorded separately (with distinct onset dates).

9.4.3.2 Action Taken for Adverse Events

For each reported adverse event, an investigator must document the action taken according to the following criteria:

- No action taken
- Concomitant medication taken
- Hospitalization or prolongation of hospitalization

- Discontinued study
- Nondrug therapy
- Other (specify)

The investigator must also document the action taken in regards to investigational product (as a result of a given adverse event) according to the following criteria:

- Dose not changed
- Investigational product interrupted
- Investigational product withdrawn
- Not applicable
- Unknown

9.4.3.3 Outcome for Adverse Events

Adverse events should be followed until resolution. For each reported adverse event, the investigator must document the outcome according to the following criteria:

- Fatal
- Not recovered/not resolved
- Recovered/resolved
- Recovered/resolved with sequelae
- Recovering/resolving
- Unknown

